2.8.2 Deaths

Summary for deaths will be provided by SOC and PT of cause of death, treatment group, and Part. Listing of all deaths will be provided.

2.8.3 Laboratory data

Laboratory data consist of hematology, biochemistry, sexual hormones, urinalysis measurements and ADA (see Section 2.8.6). Absolute values and change from baseline will be summarized for continuous laboratory parameters by visit and box plots will also be provided by visit. Frequency table of results for categorical laboratory parameters will be presented by visit. This analysis will be performed by treatment group and Part.

Shift tables using the low, normal, high/low, or high classification (except for eGFR and HbA_{1c} where the categories outlined below will be applied) will be used to compare baseline to the worst on-treatment value by treatment group and Part. All data collected after first dose of

Novartis	For business use only	Page 31
SAP amendment 4		CKJX839C12301

double-blind treatment, from scheduled, unscheduled, and premature discontinuation visits in each part will be used to determine the worst on-treatment value.

The following categories will be used for eGFR and HbA1c:

- For eGFR, the categories will be <30 mL/min/1.73m²; ≥ 30 to <60 mL/min/1.73m²; ≥ 60 to <90 mL/min/1.73m²; and ≥90 mL/min/1.73m².
- For HbA_{1c}, the categories will be <5.7%; $\ge 5.7\%$ to <6.5%; and $\ge 6.5\%$.

The shift table dealing with the fasting plasma glucose parameter will require the lab sample to be taken fasting. Samples taken while the subject was not fasted will not be analyzed.

For selected laboratory tests, the number and percentage of patients meeting the clinically notable criteria at any time, considering all data collected after first dose of double-blind treatment, from scheduled, unscheduled, and premature discontinuation visits, will be summarized by laboratory parameter and treatment group and Part. The worst post-baseline value will be used for this analysis. Notable criteria are defined in Appendix 5.5. Clinically notable criteria will be considered met when both of the following occur:

- Post-baseline value meets the clinically notable criteria.
- Baseline value does not meet the clinically notable criteria.

Furthermore, the number and percentage of participants meeting notable criteria in liver function tests (LFT) will be summarized by treatment and Part considering on-treatment data from scheduled, unscheduled, and premature discontinuation visit. LFT criteria are defined in Appendix 5.5.

The baseline value is the last value prior to the first dose of double-blind treatment.

All laboratory data will be listed by treatment group, participant, and visit/time and if normal ranges are available, abnormalities will be flagged.

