• Evaluate the safety and tolerability profile of inclisiran, compared to placebo (for Year 1) and long-term (up to Day 720), in adolescents (aged 12 to <18 years) with HeFH	 Incidence, severity and relationship to study drug of treatment-emergent adverse events (AEs) and serious adverse events (SAEs); vital signs; laboratory parameters; anti-drug antibodies (ADA) measurement; growth (height, weight, body mass index (BMI)); pubertal development (steroid hormones and Tanner staging) 		

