5.2 Exclusion criteria

Participants meeting any of the following criteria are not eligible for inclusion in this study.

- 1. Previous treatment (within 90 days of screening) with monoclonal antibodies directed towards PCSK9
- 2. (i) Active liver disease defined as any known current infectious, neoplastic, or metabolic pathology of the liver or (ii) unexplained alanine aminotransferase (ALT), aspartate aminotransferase (AST) elevation >3x ULN, or total bilirubin elevation >2x ULN (except patients with Gilbert's syndrome) at screening confirmed by a repeat measurement at least 1 week apart
- 3. Females who are pregnant or nursing, or who are of child-bearing potential, defined as all women physiologically capable of becoming pregnant (e.g. are menarchal) **unless** they agree to abstinence or, if sexually active, agree to the use of effective methods of contraception during dosing of study treatment. Female participants of child-bearing potential, who are or might become sexually active, must be informed of the need to prevent pregnancy during the study. The effective contraception methods are:
 - Barrier method: Condom or Occlusive cap (e.g. diaphragm or cervical/vault caps). For UK sites only (if applicable): with spermicidal foam/gel/film/cream/ vaginal suppository
 - Use of oral, injected or implanted hormonal methods of contraception or placement of an intrauterine device (IUD) or intrauterine system (IUS) or other forms of hormonal contraception that have comparable efficacy (failure rate <1%), for example hormone vaginal ring or transdermal hormone contraception
 - The decision on the contraceptive method should be reviewed at least every 3 months to evaluate the individual need and compatibility of the method chosen
 - If local regulations deviate from the contraception methods listed above to prevent pregnancy, local regulations apply and will be described in the informed consent form (ICF)
 - Adolescent females who have not reached menarche are exempt from the above requirements; however, to be eligible for inclusion in the study, they must be willing to comply with the above requirements if they gain child-bearing potential during the study
- 4. Any uncontrolled or serious disease, or any medical or surgical condition, that may either interfere with participation in the clinical study, and/or put the participant at significant risk (according to investigator's [or delegate's] judgment) if he/she participates in the clinical study

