8.4.1 Laboratory evaluations

Specimens will be obtained at the time points detailed in the Assessment Schedule (Table 8-1). Details on what is included in hematology, chemistry, sexual hormones, and urinalysis laboratory evaluations are provided in Table 8-3. Efficacy laboratory assessments (e.g. LDL-C) are described in Section 8.3.

Central laboratory(ies) will be used for analysis of all specimens collected, with the exception of urine pregnancy tests, which will be done locally (using testing materials supplied by the central laboratory). Serum pregnancy tests at screening will be done by the central laboratory. Details on the collections, shipment of samples and reporting of results by the central laboratory are provided to investigators in a Laboratory Manual.

Clinically notable laboratory findings are defined in Section 16.2 (Appendix 2).

A table, which provides the maximum, allowable blood-draw volumes by weight, can be found in Section 16.7 (Appendix 7). The Laboratory Manual will also provide details about prioritization when blood volume is restrictive.

Test Category Test Name		
Hematology	Hemoglobin, hematocrit, red blood cell (RBC) count, mean cell hemoglobin (MCH), mean corpuscular volume (MCV), mean corpuscular hemoglobin concentration (MCHC), white blood cell (WBC) count with differential (neutrophils, basophils, eosinophils, monocytes, lymphocytes), platelet coun	
Chemistry	Full chemistry:	
	AST, ALT, ALP, GGT, total bilirubin, direct and indirect bilirubin (if total bilirubin >2xULN), C(P)K, bicarbonate, uric acid, creatinine, blood urea nitrogen (BUN), eGFR*, sodium, potassium, calcium, phosphate, chloride, albumin, total protein, glucose (fasting)**, HbA _{1C}	
	Limited chemistry:	
	ONLY: AST, ALT, ALP, GGT, total bilirubin [fractionated bilirubin (if total bilirubin >2x ULN)], C(P)K, creatinine, eGFR*, glucose (fasting)**, HbA _{1C}	
Anti-drug antibodies	see Section 8.4.1.1	
Sexual hormones	Gonadal hormones (estradiol for females and testosterone for males), luteinizing hormone (LH), follicle-stimulating hormone (FSH), cortisol and dehydroepiandrosterone (DHEA)	
Urinalysis	Dipstick measurements for: specific gravity, pH, glucose, protein (total), ketones, bilirubin, urobilinogen, nitrite, hemoglobin (blood), leukocytes esterase	
	If dipstick measurement results are positive (abnormal), microscopic examination will be performed	
Pregnancy test	Serum / Urine pregnancy test (see Section 8.4.3)	
Other	Tryptase (only as required***)	

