Baseline and change from baseline in height, weight, and BMI will be assessed using age- and sex-adjusted z-scores and summarized by treatment group.

Clinical laboratory evaluations

Summary statistics will be provided by treatment group and visit. Shift tables using the low, normal, or high classification will be used to compare baseline to the worst on-treatment value by treatment group for Part 1 and overall. The number (and percentage) of participants meeting clinically significant criteria will be provided by treatment group for Part 1 and overall.

Immunogenicity

[figure not shown]
ADA evaluations, including treatment emergent ADA findings, will be summarized by treatment group, participant, and visit. Additional analyses may be performed to describe the relationship between ADA and other study findings and will be detailed in the SAP.

Other safety evaluations

Baseline Tanner stage will be summarized by treatment group. Shift from baseline in Tanner stage and menarche in female participants without menarche at baseline will be summarized by treatment group.

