2.8.7 Other safety evaluation

Shift from baseline in Tanner stage will be summarized by sex, treatment, visit and Part. Additionally, shift in menarche status from baseline will be summarized by visit and treatment group and Part. Mean and SD of age of the participants in each of category of shift table will be provided. Listing will be provided.

In cases where following a Tanner stage 5 the data of the next visit are missing, they will be imputed as Tanner stage 5 (as the protocol does not mandate to repeat the Tanner stage assessment once Tanner stage 5 has been reached). Similarly, menarche data will be imputed as yes if the previous assessment was yes for menarche and data are missing at the next visit.

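### LH, FSH, DHEA and cortisol are summarised with boys and girls pooled, although the same SAP splits Tanner stage by sex and adjusts growth for sex

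*SAP*

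**What the plan says.** Protocol Table 2-1 includes this among the safety endpoints: "pubertal development (steroid hormones and Tanner staging". Protocol 8.4.4.1 counts the sexual hormones, with height, weight, menarche and Tanner staging, among the assessments of pubertal development. The panel in Protocol Table 8-3 measures estradiol in females and testosterone in males, and LH, FSH, cortisol and DHEA without restriction by sex. Table 8-1 schedules it on Days 1, 330 and 720.

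The SAP analyses the panel under its general laboratory rules (2.8.3): "Laboratory data consist of hematology, biochemistry, sexual hormones, urinalysis measurements and ADA". The rule for continuous parameters is "Absolute values and change from baseline will be summarized for continuous laboratory parameters by visit and box plots will also be provided by visit", and "This analysis will be performed by treatment group and Part". Low/normal/high shift tables in the same section are also by treatment group and Part. Protocol 12.5.2 says no more: "Summary statistics will be provided by treatment group and visit". Neither text names sex for laboratory summaries.

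Elsewhere the SAP does take account of sex. In 2.8.7, "Shift from baseline in Tanner stage will be summarized by sex, treatment, visit and Part". In 2.8.5, height, weight and BMI are assessed with and without age- and sex-adjusted z-scores. The gender subgroup for safety (2.2.1, Table 2-3) applies to treatment-emergent adverse events only.

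**The concern.** The hormones and Tanner stage belong to one stated safety endpoint, but only Tanner stage is shown by sex. If the typical level of a hormone differs between boys and girls, a pooled mean, SD or box plot describes a mixture that fits neither sex. The spread widens, so a modest drug-related shift is harder to see. Sex is not a stratification factor (Protocol 6.3.2 stratifies by age only), so an accidental difference in sex mix between arms moves the pooled means apart with no drug effect.

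Day 330 is the only post-baseline hormone value with a concurrent placebo arm. Day 720 falls in the single-arm period. The Part 1 table is therefore the trial's one controlled look at these hormones.

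**Working it through.** The documents state no hormone mean, SD or reference range, so there is no plan figure to reproduce. The first step is a reading of the texts; the rest illustrates size.

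**1. Which analytes are pooled.**
- Estradiol and testosterone: one sex each by sampling (Protocol Table 8-3), so not pooled.
- LH, FSH, DHEA, cortisol: both sexes sampled, and no sex split in SAP 2.8.3, Protocol 12.5.2 or SAP Table 2-3, so pooled as written.

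**2. Inputs.**
- N = 141 enrolled, randomized 2:1 (SAP 1.1). An exact 2:1 split gives 141 × 2/3 = 94 and 141 − 94 = 47.
- Share of boys p = 0.5: assumed.
- d = difference between the sex means in within-sex SDs: assumed, shown at 1 and 2.

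**3. Spread of absolute levels.** Pooled variance = within-sex variance × (1 + p(1 − p)d²), which at p = 0.5 is 1 + d²/4.
- d = 1: variance × 1.25; SD × √1.25 = 1.118, about 12% larger.
- d = 2: variance × 2; SD × √2 = 1.414, about 41% larger.
- In information terms, 141 pooled participants are worth about 141/1.25 = 113 at d = 1 and about 70 (141/2) at d = 2.

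**4. Chance sex imbalance.** SE of the difference in share of boys = √(0.25 × (1/94 + 1/47)) = 0.089, about 9 percentage points; 95% range about ±17.5 points. An imbalance of one SE shifts the difference in mean level by 0.089 × d: about 0.09 within-sex SD at d = 1 and 0.18 at d = 2.

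**5. That shift against ordinary noise.** Without a sex difference, the SE of an arm difference is √(1/94 + 1/47) = 0.179 within-sex SD. Pooled, it is 0.179 × 1.118 = 0.20 at d = 1 and 0.179 × 1.414 = 0.25 at d = 2. A one-SE sex imbalance is therefore 0.089/0.20 = 0.45 of a pooled SE at d = 1 and 0.179/0.25 = 0.7 at d = 2. Steps 3 and 4 are not separate harms: √(0.179² + 0.089²) = 0.20, so the pooled SE at d = 1 already contains the chance imbalance.

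**6. Change from baseline.** SAP 2.8.3 also summarises change, in which any stable sex difference cancels. The relevant d is then the sex difference in mean change, probably smaller than for levels. The documents give nothing from which to estimate it.

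**The case against.** The case against making much of this is substantial.

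- **The most direct pubertal outcomes are handled well.** Tanner shifts are by sex, menarche is summarised, growth has z-scores, and estradiol and testosterone are sex-specific. This stands. It confines the point to four analytes. Two of them, LH and FSH, are not steroids and so fall outside the literal wording of Table 2-1, although Protocol 8.4.4.1 brings the whole panel into the pubertal assessment.
- **Part 1 is randomized with a concurrent placebo arm, stratified at 15 years.** Sex, puberty and contraceptive use are balanced on average. This stands. A reader might infer that the hormone comparison is confounded by sex mix or normal puberty; the design does not support that.
- **The tables are descriptive and no test is planned.** True, so power figures would answer a question the SAP does not ask. The tables are still the planned means of reading this part of the endpoint.
- **Listings and shift tables help.** In part. SAP 2.8.3 flags abnormal values where normal ranges exist, but does not say the ranges are specific to sex or age, and SAP Table 5-1 has no hormone criterion.
- **Pooling is inferred from silence.** The table shells, which are not available here, might add a split. SAP 2.8.3 does not require one.

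A reader might also want a split by baseline Tanner stage (below 5 versus 5), or removal of samples taken on hormonal contraception, which Protocol 5.2 lists as an accepted method. Neither is well supported. Protocol 8.4.4.1 records a stage for each characteristic, so the cut at 5 is undefined, and crossing it with sex would leave about 47/4 = 12 placebo participants per cell if evenly spread. Contraception may start after randomization, so excluding those samples conditions on a post-randomization event and could itself distort the comparison. The documents do not indicate how many girls would be affected.

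**Conclusion.** The point holds for LH, FSH, DHEA and cortisol: as written they are pooled across sex, out of line with how the SAP treats Tanner stage and growth. In Part 1 the cost is reduced sensitivity and exposure to chance imbalance, not systematic bias. For absolute levels the SD is inflated by about 12% at d = 1 and 41% at d = 2. This rests on an assumed even sex mix, an exact 94:47 split and assumed values of d; the effect on change from baseline is probably smaller and cannot be quantified from the documents.

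It would go too far to say that the hormone part of the pubertal-development objective is obscured as a whole. The gonadal steroids are already separated by sex, and the efficacy analyses are untouched. This is a worthwhile improvement in the readability of a safety endpoint.

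**What to change.** In SAP 2.8.3, state that summary statistics, box plots and shift tables for LH, FSH, DHEA and cortisol will be presented by sex within treatment group, visit and Part. Leave estradiol and testosterone as they are. Do not add a baseline Tanner split or exclude samples taken on hormonal contraception; at most, flag contraceptive users in the listing from the concomitant-medication record.

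Amendment 4 of the SAP (3-Dec-2024) reports actual enrollment and states that the full analysis and safety sets are equal in Part 1, which suggests, without proving, that Part 1 was already locked. If it was, label the Part 1 tables post hoc, as the SAP appendix does for the added PCSK9 analysis.

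The cost is SAP wording and a few descriptive tables from data already collected, with no effect on alpha or design. The drawback is smaller cells: at an even sex mix, about 47/2, or 23 to 24, placebo participants per sex.

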10.2.3 Other safety monitoring

The frequency and severity of the AEs listed below will be monitored during the study. They will be reviewed by the DMC at regular intervals.

- ISRs (see also Section 8.4.4.3), hypersensitivity reactions and immune-mediated reactions
- Hepatobiliary AEs and liver-related biochemical abnormalities (see also Section 6.5.2.1 and Section 10.2.1)
- Musculoskeletal AEs and muscle-related biochemical abnormalities (e.g. C(P)K)
- Neurological or psychiatric AEs
- New onset of diabetes or worsening of glycemic control in diabetics (see also Section 8.4.4.5)

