5.5 Laboratory parameters derivations

The following table shows the criteria for clinically notable laboratory values. Not all parameters have notable criteria defined:

Table 5-1 Clinical notable criteria for selected laboratory tests

	Notable post-baseline value
Hematology	
Hemoglobin	$\leq 10 \text{ g/dL}$
Hematocrit	$\leq 0.8 \text{ x LLN}$
WBC count / Leukocytes	$\leq 2.8 \text{ x } 10^9/\text{L} \text{ or } \geq 16 \text{ x } 10^9/\text{L}$
Platelet count	$\leq 75 \text{ x } 10^9/L \text{ or } \geq 700 \text{ x } 10^9/L$
Clinical chemistry	
C(P)K	>5 x ULN
	>5 and $\leq 10 \text{ x ULN}$
	>10 and ≤20 x ULN
	>20 x ULN
Creatinine	\geq 50% increase from baseline (not >2 mg/dL)
	>2 mg/dL
	\geq 50% increase from baseline or >2 mg/dL
eGFR	<30 mL/min/1.73m2
	\geq 30 to <60 mL/min/1.73m2
	≥ 60 to <90 mL/min/1.73m2
Glucose	≥100 to <126 mg/dL
	≥126 mg/dL
HbA1C	≥5.7% to <6.5%
	≥6.5%

Novartis	For business use only	Page 42
SAP amendment 4		CKJX839C12301

Table 5-2	Notable liver function to	est values
		col valueo

Criterion
ALT > 3 x the upper limit of normal range (ULN)
ALT > 5 x ULN
ALT > 8 x ULN
ALT > 10 x ULN
ALT > 20 x ULN
AST > 3 x ULN
AST > 5 x ULN
AST > 8 x ULN
AST > 10 x ULN
AST > 20 x ULN
ALT or AST > 3 x ULN
ALT or AST > 5 x ULN
ALT or AST > 8 x ULN
ALT or AST > 10 x ULN
ALT or AST > 20 x ULN
Total bilirubin > 2 x ULN
TBL >2xULN & DBL >ULN
TBL >2xULN & DBL >2xULN
ALP > 2 x ULN
ALT or AST > $3 \times ULN$ and total bilirubin > $2 \times ULN$
ALT or AST > 5 x ULN and total bilirubin > 2 x ULN
ALT or AST > 8 x ULN and total bilirubin > 2 x ULN
ALT or AST > 10 x ULN and total bilirubin > 2 x ULN
ALT or AST > 20 x ULN and total bilirubin > 2 x ULN
ALT or AST > 3 x ULN and Total Bilirubin > 2 x ULN and ALP < 2 x ULN (Hy's law)

ALT = alanine aminotransferase, AST = aspartate aminotransferase, ALP = alkaline phosphatase, DBL = Direct bilirubin

When a criterion contains multiple laboratory parameters, the criterion will only be considered to have been met when all conditions occur within a 3-day window.

Novartis	For business use only	Page 43
SAP amendment 4		CKJX839C12301

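### The baseline condition for clinically notable laboratory values (SAP 2.8.3) miscounts moves between the bands of HbA1c, glucose, eGFR and C(P)K, whichever way it is read

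*SAP*

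**What the plan says.** SAP 2.8.3 sets two conditions for a clinically notable laboratory value: "Post-baseline value meets the clinically notable criteria" and "Baseline value does not meet the clinically notable criteria". It adds that "The worst post-baseline value will be used for this analysis" and that the counts "will be summarized by laboratory parameter and treatment group and Part".

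The criteria are in SAP 5.5, Table 5-1. Several parameters have more than one row:

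- **Glucose:** "≥100 to <126 mg/dL", then 126 mg/dL or more.
- **HbA1c:** 5.7% to below 6.5%, then 6.5% or more.
- **eGFR:** "<30 mL/min/1.73m2", then 30 to below 60, then 60 to below 90.
- **C(P)K:** a cumulative row above 5 x ULN, then three exclusive bands, the middle one being ">10 and ≤20 x ULN".

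The haematology criteria have one entry per test. The liver criteria (Table 5-2) are described separately, without this baseline condition. Neither group is affected.

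**The concern.** A rule of the form *met after baseline, not met at baseline* works for a single threshold. It does not work for exclusive bands, because leaving one band usually means entering another. The SAP leaves open whether the criteria in the baseline condition are the row being tabulated or all rows of that parameter, and either choice gives some wrong counts.

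What is at stake is one descriptive safety table. Two programmers could produce different counts from the same data. The HbA1c rows could also disagree, without explanation, with the HbA1c shift table, which uses the same cut-offs and the same worst value.

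**Working it through.** The plan states no figure to reproduce. The first two steps and the last need only the documents; the third rests on assumed distributions.

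**1. Inputs.** The rule comes from SAP 2.8.3 and the bands from Table 5-1. Protocol 5.2 excludes only HbA1c above 10.0%, so a baseline of 6.5% to 10.0% is possible. Protocol 5.1 requires eGFR above 30 at screening, so a baseline below 30 is essentially ruled out. Protocol Tables 8-1 and 8-3 give six post-baseline HbA1c and glucose samples in Part 1 (Days 30, 90, 150, 270, 330, 360). SAP 1.1 gives 141 participants.

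**2. Enumeration.** *Row by row* means the baseline is not in that same row. *Per parameter* means the baseline is in no row of that parameter.

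| Baseline band | Worst later band | True direction | Row by row | Per parameter |
|---|---|---|---|---|
| HbA1c <5.7 | ≥6.5 | worse | counted | counted |
| HbA1c 5.7–<6.5 | ≥6.5 | worse | counted | **dropped** |
| HbA1c ≥6.5 | 5.7–<6.5 | better | **counted** | not counted |
| Glucose 100–<126 | ≥126 | worse | counted | **dropped** |
| Glucose ≥126 | 100–<126 | better | **counted** | not counted |
| eGFR 60–<90 | 30–<60 or <30 | worse | counted | **dropped** |
| eGFR 30–<60 | <30 | worse | counted | **dropped** |
| eGFR 30–<60 | 60–<90 | better | **counted** | not counted |
| C(P)K >5–10x | >10–20x or >20x | worse | counted | **dropped** |
| C(P)K >10–20x | >20x | worse | counted | **dropped** |
| C(P)K >10–20x or >20x | any milder notable band | better | **counted** | not counted |

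Row by row keeps all true worsening and adds some improvers. Per parameter adds no improvers and loses every upward move that starts inside a notable band.

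**3. Size, under assumptions.** The documents give no HbA1c or glucose distribution. Each scenario used 1,000,000 simulated participants, with the worst of six values compared with baseline.

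Share dropped per parameter = (new top-band cases whose baseline was in the middle band) / (all new top-band cases).

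- HbA1c (mean 5.2–5.4%, between-person SD 0.25–0.35, within-person SD 0.1–0.2, individual drift SD 0–0.4): 27% to 100%, and at least 90% in 10 of 24 scenarios.
- HbA1c with 0.2% to 1% abrupt onset unrelated to baseline: 17% to 77%.
- Fasting glucose (mean 86–94 mg/dL, between-person SD 5–7, within-person SD 5–9, drift SD 0–6): about 24% to 99% where there were enough cases to judge.

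Number dropped = 141 × rate of new top-band cases × share dropped:

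- HbA1c, highest scenario: 141 × 0.05917 × 0.652 = 5.4.
- HbA1c, a middling one (mean 5.4, SDs 0.25, 0.2, 0.2): 141 × 0.00731 × 0.758 = 0.8.
- Glucose, highest scenario: 141 × 0.03020 × 0.637 = 2.7.
- Glucose, a middling one (mean 90, SDs 7, 7, 6): 141 × 0.00450 × 0.669 = 0.4.

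A second set assumed wider between-person spread and a common upward drift (glucose mean 92–95, between-person SD 9–12, within-person SD 6–7, drift 0–10 mg/dL; HbA1c mean 5.3–5.4%, SD 0.35–0.5, within-person SD 0.15–0.2, drift 0–0.2). It gave 0.5 to 22 new cases at 126 mg/dL or more (88–98% dropped per parameter) and 0.3 to 12 at 6.5% or more (96–100% dropped). In this set the row-by-row reading wrongly counted about 0.01 to 0.5 improvers per 141.

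**4. Where dropped cases would still appear.**

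- *HbA1c and eGFR:* in the SAP 2.8.3 shift tables, which use these cut-offs and the worst value. For HbA1c, also in the new-onset diabetes analysis of 2.8.4, where one value of 6.5% or more is enough.
- *Glucose:* the 2.8.4 shift categories and the new-onset component need 126 mg/dL or more on two consecutive occasions. If two consecutive values fall in different categories, HbA1c decides. The 2.8.3 glucose shift table is low/normal/high. A single value of 126 or more from the 100–<126 band need not be shown as such in any of these.
- *C(P)K:* the shift table is low/normal/high, so a move from >5–10x to >20x ULN reads as high to high.

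**The case against.** **The layout favours the row-by-row reading.** Creatinine has two rows and then their union, and C(P)K has a cumulative row plus sub-bands. Such rows make sense only if each is counted separately. On that reading all true worsening is counted, and the error needs a participant already in a worse band whose worst later value is milder. This has force and is the main reason the point is small. It does not settle the text, since 2.8.3 also speaks of summarising by parameter and never states the unit of the baseline condition.

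**The signal is captured elsewhere.** This largely stands. SAP 2.8.4 is the detailed glycaemic analysis and reports participants with impaired baseline separately. Protocol 8.4.4.5 makes HbA1c of 6.5% or more reportable as an adverse event in participants without a diabetes history, and full listings are planned. The exceptions are the single high glucose value and the upward C(P)K move, which would show in listings but not necessarily in another categorical table.

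**Stronger readings that the documents do not support.** A reader might infer that nearly all participants newly in the diabetic range would be lost. That follows only under some assumed distributions. The wider set above puts roughly 23–36% of adolescents at 100 mg/dL or more at baseline and has no abrupt onset; other plausible inputs take the HbA1c share down to 17%. Moves straight from normal are always kept.

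A reader might also infer that DMC oversight is weakened, because Protocol 10.2.3 lists "New onset of diabetes or worsening of glycemic control in diabetics" among the topics the DMC reviews. That list concerns adverse events. SAP 2.1 places the DMC analyses in the charter and a separate DMC SAP, so nothing shows that this table reaches the DMC.

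**Conclusion.** The defect holds, within limits. For HbA1c, glucose, eGFR and the C(P)K sub-bands, the baseline condition is ambiguous and miscounts under either natural reading. That conclusion needs no distributional assumption.

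Its size does. Improvers wrongly counted should be rare, although the documents give no number of participants entering with diabetes. The share of worsening participants dropped under the per-parameter reading cannot be derived from the documents. Absolute counts are probably small, and would grow mainly if values drifted upward across the group.

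The primary and key secondary analyses are untouched, and the glycaemic safety assessment as a whole is not lost. This is a minor correction to one descriptive safety table.

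**What to change.** In SAP 2.8.3, add one sentence for the banded parameters (HbA1c, glucose, eGFR and the C(P)K sub-bands): a participant is counted in a row only when the worst post-baseline value falls in that band and the baseline value is in neither the same nor a more severe band.

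Alternatively, make the Table 5-1 rows cumulative using the thresholds already there, each with its own baseline check: HbA1c ≥5.7% and ≥6.5%; glucose ≥100 and ≥126 mg/dL; eGFR <90, <60 and <30; C(P)K >5x, >10x and >20x ULN. Either version counts every worsening move in the enumeration and no improving one.

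Then rerun the table. The SAP is filed as a study report appendix and mentions an analysis added after the Part 1 lock, so outputs may already exist. If so, state which reading was applied. The cost is one sentence and a small programming change; no new data are needed.
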